1. PROTOCOL SYNOPSIS

Studies in animals have shown that both long-chain n-3 polyunsaturated fatty acids (PUFA) and a bacterial metabolite of dietary fiber (butyrate) may reduce colon tumor formation, and that the two in combination are even more effective than either alone. Several different mechanisms of action have been suggested. In humans, some epidemiologic studies suggest that people who consume high-fiber diets or use n-3 PUFA supplements may have a lower risk of colorectal cancer, but there are currently no controlled dietary interventions evaluating the combined effects of these two dietary constituents on colorectal cancer risk factors in humans. We will test the combination of n-3 PUFA and fiber on gene expression in colon cells that are part of the pathways important to cancer risk and will seek to understand how variation in the gut bacterial community may affect response to intervention.

Design: A randomized, placebo-controlled, double blinded, crossover dietary intervention

Sample Size: Recruitment of 40 participants with the goal of having 30 complete study measures.

Participants: Men and women

Selection: Individuals from the Greater Seattle area who are normal to overweight (BMI of 18-30 kg/m²) and between the ages of 50-75, who typically consume diets with 20g fiber or less per day. We will recruit U.S. racial minorities at an overall level of 32%, which mirrors the minority distribution in Seattle/King County

Exclusion: The exclusion criteria will address a mix of medical and practical issues: 1) chronic medical illness, history of gastrointestinal disorders (e.g., ulcerative colitis, Crohn disease, celiac sprue, HNPCC, familial adenomatous polyposis, pancreatic disease, previous gastrointestinal resection, radiation or chemotherapy, and cancer (other than non-melanoma skin cancer); 2) weight change greater than 4.5 kg within past year; 3) oral or IV antibiotic use within the past 3 months; 4) regular use of aspirin or NSAIDs; 5) smoking; 6) known allergy to fish; 7) intention to relocate out of study area within next 4 months; 8) abnormal liver/kidney function as ascertained at a baseline blood draw.

Intervention: a) Placebo and b) Supplemental soluble fiber (35 g/d) + supplemental n-3 PUFA (6 g/d eicosapentaenoic acid (EPA) and docosahexaenoic acid (DHA).

2. BACKGROUND/SIGNIFICANCE

Diet is an important risk factor for colorectal cancer (CRC) and several dietary constituents implicated in CRC are modified by gut microbial metabolism. Microbial fermentation of dietary fiber produces short chain fatty acids (SCFA), e.g., acetate, propionate, and butyrate. Dietary fiber has been shown to reduce colon tumors in animal models and, *in vitro*, butyrate influences cellular pathways important to cancer risk. Further, work from our group suggests that the combined effects of butyrate and long chain omega-3 polyunsaturated fatty acids (n-3 PUFA) found in cold-water, oily fish, may enhance the chemopreventive potential of these dietary constituents. We postulate that the relatively low intakes of n-3 PUFA and fiber in Western populations and the failure to address interactions between these dietary components may explain why chemoprotective effects of n-3 PUFA and fermentable fibers have not been detected consistently in prospective cohort studies. We hypothesize that the combined effects of n-3 PUFA supplementation and supplemental highly fermentable fiber will alter critical pathways important to CRC prevention, particularly intrinsic mitochondrial-mediated programmed cell death resulting from the accumulation of lipid reactive oxygen species (ferroptosis), cell proliferation, and the eicosanoid/inflammation pathways.

Gut bacteria ferment dietary fiber to butyrate and other SCFA.¹⁻¹⁴ Butyrate is a potent histone deacetylase inhibitor^{15, 16} associated with reduced CRC risk.¹⁷⁻¹⁹ Work from our group using preclinical models suggests that *combined effects of fiber-derived butyrate and n-3 PUFA in fish oils act synergistically* to enhance the chemopreventive potential above and beyond the contribution of butyrate alone, in part, by altering the glutathione peroxidase-4 (GPX-4)-dependent redox environment in the cell and increasing programmed cell death (ferroptosis).²⁰⁻³⁰ These results agree with a recent prospective, nested case-control study demonstrating significant CRC risk reduction among pescovegetarians, whose diets were high in both dietary fiber and n-3 PUFA-rich fish (HR: 0.57; 95% CI: 0.40, 0.82).³¹ We hypothesize that the combined effects of 35 g supplemental fiber, high in soluble fibers, and 6 g supplemental long chain n-3 PUFA (DHA + EPA) will alter pathways important to CRC prevention.

This is a randomized, controlled crossover pilot study in 40 healthy men and women (50-75 y) to compare supplemental soluble fiber (35 g/d) + supplemental n-3 PUFA (6 g/d EPA+DHA), in quantities mirroring mean daily intakes associated with lower CRC risk, with a maltodextrin and corn oil control (placebo). Stool samples will be collected at the beginning, middle (day 15), and end of each of the two 30-day intervention periods. Using a novel, cost-effective, non-invasive approach, we will evaluate differences in global gene expression signatures in the stool exfoliome (i.e., sloughed colonic epithelial cells in stool) using RNA-Seq.³² We will focus on pathways related to colonic cell proliferation and apoptosis/ferroptosis, cell phenotype, and inflammatory response. Further, we will evaluate changes in gut microbial functional genes involved in butyrate production using droplet digital PCR (ddPCR). The collection of multiple samples over the intervention periods will provide a critical measure of longitudinal changes in response to the supplemental n-3 PUFA and fermentable fiber.

This pilot will be the first in humans to integrate and characterize the relationships between n-3 PUFA and fermentable fiber exposure that modulate programmed cell death and other CRC-related cell-signaling pathways through metabolic activities of the gut microbiome. Results of this controlled intervention will help to translate the current mechanistic knowledge from preclinical animal models to humans and to inform approaches for CRC prevention. Interrogating the stool exfoliome is a novel, cost-effective, non-invasive approach to studying effects of interventions on the human gut.

3. SPECIFIC AIMS, OBJECTIVES, ENDPOINTS:

Aim 1: To test in a pilot feasibility study, in humans, effects of supplemental dietary fiber (35 g) and EPA+DHA (6 g) vs placebo on mRNA expression in exfoliated colonic cells. We hypothesize that fiber and n-3 PUFA supplementation will uniquely influence colonocyte proliferation and programmed cell death-related gene expression and signaling pathways.

Aim 2: To test whether response to the intervention differs by gut microbial functional capacity related to fiber fermentation. We hypothesize that changes in colonocyte gene expression will be modified by the

gut microbial capacity to ferment dietary fiber (i.e., SCFA-producing pathways), measured as butyrogenic potential. Σ (butyryl-CoA:acetate CoA-transferase (*but*) + butyrate kinase (*buk*) genes)/(total bacterial load 16S rRNA gene) assayed using digital drop PCR.

[figure not shown]
Objectives and Endpoints:

1. To determine whether the combination of supplemental dietary fiber and EPA+DHA vs placebo affects mRNA expression in exfoliated colonic cells. The endpoint is mRNA expression profiles in the exfoliome.
2. To determine whether gut microbial functional capacity related to fiber fermentation, as measured by presence of fiber-fermenting genes in stool bacteria, alters exfoliome mRNA expression response to the intervention on. The endpoint is mRNA expression profiles in the exfoliome.

Implications: This proposed pilot feasibility study will be the first controlled study in humans to integrate and characterize the relationships between n-3 PUFA and prebiotic fiber exposure that modulate programmed cell death/CRC-related cell-signaling pathways through changes in the gut microbiome. Results of this human mechanistic controlled intervention will help to translate the current mechanistic knowledge from preclinical animal models to humans and to inform approaches for CRC prevention. Also, importantly, we will further evaluate the utility of interrogating the exfoliome as a novel, non-invasive approach to studying effects of interventions on the human gut.

4. STUDY DESIGN

The study is designed as a randomized, cross-over, placebo-controlled dietary intervention of supplemental soluble fiber and supplemental n-3 PUFA compared to corn oil and maltodextrin control. We will randomize participants to one of the two treatment orders, either supplemental fiber and fat first followed by the placebo in the second period or the placebo first followed by supplemental fiber and fat. Each treatment will be 30 days in duration with at least a 60-day washout period between treatments. Stool samples will be collected at the beginning, middle (day 15) and end of each of the two 30-day intervention periods.

It will take participants at least 4 months to complete the trial. Details of the activities and timeline:

Activity	1-2 weeks before Day 0	DAYS in Period 1					at least 2 months (washout)	DAYS in Period 2				
		0	1 - 14	15	15 - 29	30		0	1 - 14	15	15 - 29	30
Info session and consent	1											
Fasting morning blood draw*	2							6				
Collect stool												
Deliver stool & get study supplements		3						6				
Take study supplements daily												
Collect stool												
Deliver stool & get study supplements				4						7		
Take study supplements daily												
Collect stool												
Fasting morning blood draw & deliver stool						5						8

*Visit 2: If results from liver/kidney functions test are abnormal, participant will not continue with study

Study Visit # = visits to Fred Hutch
= activities at home

4.a. Fiber and Fat Supplements The active treatment period will include supplemental soluble fiber (35 g/d) + supplemental n-3 PUFA (6 g/d EPA+DHA).

Supplemental Fiber: The soluble fiber with known fermentation profiles will be provided by Tate & Lyle, a well-established food and beverage ingredient company. For placebo, we will use maltodextrin provided in the same packaging and by the same company.

Supplemental n-3 PUFA: We will use a commercial fish oil supplement (Omega Cure, Omega3 Innovations), consumed as 2 vials daily. Each vial (11.75 g oil) delivers 3 g EPA +DHA in a 1:1 ratio. For placebo, we will use equivalent amounts of corn oil in visually identical packaging provided and by the same company.

All study supplements will be in packaged as daily doses. At the study visits at the beginning and mid-point of each study period, participants will receive a box with all the supplements needed to cover the time in between visits along with instructions regarding proper storage conditions (ie. the fish oil is to be refrigerated for better preservation.)

4.b. Safety and Adverse Effects Supplemental fiber (30-45 g/d) has been well-tolerated in short and long-term interventions (4 wks to 1-10 y).³³⁻³⁶ In a study specifically designed to evaluate tolerance, individuals were given 10, 30 and 60 g/d of supplemental fiber for 7 d in addition to their regular diet. All doses were well-tolerated.³⁷ Further, the specific product we propose to use, PROMITOR® Soluble Corn Fibre (SCF), has been well tolerated by healthy volunteers at 65 g/d.^{38, 39} SCF, a glucose oligosaccharide, containing a mixture of α 1-6, 1-4, 1-3, and 1-2 glucosidic linkages, has demonstrated prebiotic effects.^{40, 41} Testing of SCF in an *in vitro* SHIME method that mimics human digestion showed that SCF is well fermented in the distal colon leading to positive effects on the GMC, and that these effects are translated to immunomodulatory properties and improved gut barrier.⁴² Long-term trials (6-27 months) designed to evaluate safety of supplemental n-3 PUFA up to 7 g/d have reported no adverse in general, and in bleeding complications specifically, even among patients at higher risk.^{43, 44} There is insufficient data to establish a tolerable upper intake for n-3 PUFA for any population group.⁴⁵

4.c. Length of intervention periods and washout: Description and rationale. Intervention Periods: Crypt turnover is 3.5 d and 4.2 d for the colon and rectum, respectively⁴⁶ and dietary n-3 PUFA are

incorporated into colonic cell membranes within 7 d.⁴⁷ 1-mo interventions with diet or aspirin result in measurable changes in colonocyte gene expression⁴⁸ and down-stream colon biomarkers.⁴⁹ Gut microbiome changes occur in 2-3 wks.^{3, 50, 51} Changes in gut mucosal cancer-risk biomarkers, the microbiome, and microbial metabolites were also seen in a short-term 2-wk intervention of fat and fiber.⁵² We hypothesize that changes in the gut microbiome influence colonic gene expression, thus conservatively we are using a 30-d period to allow sufficient time for both outcomes to change, while considering participant burden. Washout: The 60-d washout will ensure that residual intervention effects from the previous period are eliminated. As mentioned, the gut epithelium and microbiome change rapidly, but blood DHA+EPA clearance requires 45 d.⁵³

4.d. Monitoring and assessing adherence. Participants will meet with study staff routinely to assess any difficulties with study adherence. n-3 PUFA are rapidly incorporated into colonic tissue.^{54, 55} and there is high correlation between membrane PUFA and plasma phospholipid (PLFA) PUFA.^{56, 57} We will assess adherence to n-3 PUFA supplementation using plasma PLFA profiles (**Section C.4.a**) and by monitoring vial counts, calculating adherence % (vials supplied - vials returned/days elapsed).⁵⁸ Adherence to supplemental fiber will be monitored by study staff. Participants will be instructed to return unconsumed fiber packets for weighing and consideration in intake determination. During the intervention, participants will complete daily forms to monitor adherence to the supplements.³²

4.e. Summary of study activities and measures

Table 1. Study Activities and Measures

	Reason for Measures
Screening	
Screening questionnaire	Exclusion criteria
Information session	Informed consent
Baseline blood sample to Quest Diagnostics	Exclusion criteria (liver and kidney functions)
Health and Demographics questionnaire	Exclusion criteria
Anthropometrics	Exclusion criteria
Two Supplementation Periods	
Each 30 days each	
Cross-over (order randomly assigned) *	
Stool samples (6 total) Beginning, middle and end of each period	
For colonocytes	Global gene expression signatures in the exfoliome (using RNA-Seq)
For Microbial	Microbial DNA extraction, ddPCR and SCFA.
Bowel Habits & General Symptoms questionnaire	Intervention effects
Blood samples (4 total) Baseline & end of each period	Plasma phospholipid PUFA
Weight, Baseline & end of each period	Monitor biological changes
Daily calendar	Compliance

* In between feeding periods there will be at least 60 days washout period.

5. STUDY POPULATION/RECRUITMENT

Participants will be healthy, non-smoking men and women, ages 50-75 y, who are normal to overweight [body mass index (BMI) ≥ 18 and ≤ 30 kg/m²]. Women will be postmenopausal, with no menstrual period in 12 months. We will place ads in newspapers, distribute flyers, and use social media. A screening survey will determine eligibility (age, health, medications, habitual fiber intake); individuals will meet with the study coordinator for an info session and to obtain consent. We will measure height and weight (for BMI) and draw blood (Complete Blood Count (CBC) and Comprehensive Metabolic Panel) analyzed by Quest Diagnostics, a CLIA certified lab) will further determine eligibility.

Study information will be available online. The screening questionnaire will be downloadable. Interested persons will fill it out and send it via mail. A contact phone number and email address will also be provided for individuals who want to be mailed an information packet. Interested persons will return the completed questionnaire to the study staff, who will determine eligibility and will contact eligible persons

by phone or email to schedule a meeting. A packet containing a confirmation letter and the screening study consent form will be sent to the person prior to attending the meeting. Participants eligible to enter the intervention will meet with our staff to discuss all the details and expectations of the study, review informed consent and answer any questions they might have, and if still interested sign the consent form.

6. ELIGIBILITY CRITERIA

Inclusion: Healthy men and women aged 50-75 years who are normal-overweight (BMI of 18-30 kg/m²), non-smoking and consume fiber intakes of less than <20 g/d.

Exclusion:

1. medical conditions: hypertension requiring medication; chronic liver disease (cirrhosis, hepatitis); kidney dysfunction or disease; previous resection of stomach or intestines; history of gastrointestinal disorders: colorectal cancer or other gastrointestinal cancer, polyposis syndromes, inflammatory bowel disease (ulcerative colitis, Crohn disease), intestinal blockage requiring surgery, pancreatic disease, radiation treatment to the abdomen within past 5 years; cancer (other than non-melanoma skin cancer);
2. regular use (more than once per week) of: NSAIDs (aspirin, ibuprofen, naproxen), Coumadin (warfarin), Eliquis (apixaban), Plaviz (clopidogrel), Xarelto (rivaroxaban), Lovaza™ (prescription fish oil), blood clotting medications;
3. weight change greater than 4.5 kg within past year;
4. oral or IV antibiotic use within the past 3 months;
5. consumption of three or more alcoholic beverages a day;
6. smoking or use of cannabis products within the past year;
7. known allergy to fish or fish-containing products; allergy to Vitamin E analogues
8. intention to relocate out of study area within next 4 months;
9. abnormal clinical lab tests as ascertained at a baseline blood draw:

Ineligible if results fall outside of the following parameters based on Complete Blood Count (CBC) and Comprehensive Metabolic Panel performed by Quest Diagnostics (a CLIA certified lab).* Blood from the baseline fasting blood draw will be sent to Quest with Study IDs not names. Parameters:

White blood cell count 3,000-11,000/mm³
Platelet count 150,000-400,000 mm³
Bilirubin 0.2-1.3 mg/dL
AST 0-35 U/L
ALT 0-40 U/L
Alkaline phosphatase 20-125 U/L
Creatinine ≤ 1.2 mg/dL
Potassium 3.5-5.0 mmol/L

*We will provide participants with a copy of their lab results if these are out of the normal range – which will make them ineligible for the study. We call them with this information prior to sending them the results via mail. We will encourage them to contact their physician.

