7. SPECIMEN AND DATA COLLECTION

7.a. Blood We will obtain 10-hour fasting blood samples at the beginning and at the end of each intervention period. The first sample will be sent to QUEST Diagnostics (a CLIA certified lab) for clinical chemistries (to confirm eligibility; see Section 6 for specifics). Participants will come to the Prevention Center at the Fred Hutch where certified personnel will collect four 10-ml vacutainers of blood; for plasma and serum. Specimens will be stored at -80°C.

7.b. Stool samples at three timepoints in each intervention arm, beginning, middle and end; for : a) exfoliated colonocyte transcriptome (mRNA) analysis, and b) fecal microbiome analyses. Participants

will collect small samples of stool into vials we provide that are pre-filled with RNAlater for microbial DNA,⁵⁹ RNAsheild for exfoliated colonocyte transcriptomics,⁶⁰ and in 95% ethanol for SCFA and future metabolomics measures.⁶¹ Human transcriptome profiles are stable for at least 60 h at 4°C prior to addition of RNAsheild solution and once RNAsheild solution is added, at -80°C for at least 2 yrs.^{48, 60}

7.c. Questionnaires: Dietary Assessment We will use an established, validated food frequency questionnaire (FFQ) to characterize food and nutrient intakes of the study participants over the 3 months prior to baseline to characterize habitual diets (typically low in n-3 PUFA and fiber and high in n-6 PUFA). **Health and Demographics** will also be collected. A **General Symptoms and Bowel Habits Questionnaire** will also be provided every time participants collect stool- this is a useful tool to determine intervention effects.

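### Section 6 excludes only prescription fish oil and sets no rule for participants' own n-3 supplements, so users of half the tested intervention can enrol and their use is uncontrolled across periods

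*Combined protocol and SAP*

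**What the plan says.** The inclusion criteria in section 6 limit background fibre: participants must be "non-smoking and consume fiber intakes of less than <20 g/d". They set no limit on n-3 intake or fish consumption.

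Exclusion 2 covers "regular use (more than once per week) of: NSAIDs (aspirin, ibuprofen, naproxen" and several anticoagulant or antiplatelet drugs, and ends with "Lovaza™ (prescription fish oil), blood clotting medications". This is the only n-3 product named. The exclusion list in the synopsis names none. The only other fish-related criterion is "known allergy to fish or fish-containing products; allergy to Vitamin E analogues".

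Section 5 describes screening as follows: "A screening survey will determine eligibility (age, health, medications, habitual fiber intake". Supplements and n-3 intake are not mentioned. Section 7.c uses the food frequency questionnaire "to characterize habitual diets (typically low in n-3 PUFA and fiber and high in n-6 PUFA", so low n-3 intake is expected but not required. Section 8.a measures plasma phospholipid EPA and DHA on days 0 and 30 as an adherence check, with no eligibility threshold. The covariates that section 9.b gives as examples are age, sex and BMI; baseline n-3 status is not among them.

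Section 4.c gives 45 days for EPA and DHA to clear from blood and sets a 60-day washout to remove the previous period's effects. Section 4.b rests its n-3 safety case on "Long-term trials (6-27 months) designed to evaluate safety of supplemental n-3 PUFA up to 7 g/d".

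**The concern.** One of the two active components has a background limit and the other does not. The product that is excluded supplies the same fatty acids as products sold without prescription, so the entry separates volunteers by how they obtain n-3 rather than by whether they take it. The synopsis itself notes that "people who consume high-fiber diets or use n-3 PUFA supplements may have a lower risk of colorectal cancer". That is epidemiological background and not an eligibility statement, but it shows that the plan is aware of such users.

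Three things are at stake. First, users may respond less to the study oil if the response levels off at higher intake, which dilutes the mean effect in a small pilot. Second, a change in own use during the roughly four months of participation alters the n-3 contrast between periods. Vial counts would miss this because they record only study vials. Third, own use adds to the 6 g/d study dose, and the plan does not relate that total to the range it cites for safety.

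**Working it through.** **Inputs from the plan.** Study dose: 2 vials × 3 g = 6 g/d EPA+DHA (section 4.a), which reproduces the stated figure. Clearance 45 days, periods 30 days, washout at least 60 days (sections 4 and 4.c). Power basis: n = 30, two-sided paired t-test, alpha 0.05, at least 80% for effect sizes above 0.5 (section 9.c).

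**Assumptions (not in the documents).** Own-product intake x = 0.3 to 2 g/d EPA+DHA. Proportion of completers who are users p = 10% to 20%. Users' effect relative to non-users r = 0.5, with r = 0 as the worst case.

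**Step 1: steady use.** Intake is x on placebo and 6 + x on active. Contrast = (6 + x) − x = 6 g/d for any x. An additive response is not biased.

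**Step 2: use that changes between periods.** If own oil is dropped only during the active period, the contrast is 6 − x: 5.7 g/d at x = 0.3 (0.3/6 = 5% less) and 4 g/d at x = 2 (2/6 = 33% less). This concerns the n-3 component only; the 35 g/d fibre contrast is unchanged.

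**Step 3: use that stops just before day 0.** Clearance of 45 days outlasts the 30-day first period. Period 2 starts at least 30 + 60 = 90 days after day 0, when clearance is complete. Residual n-3 therefore sits in period 1 only. It raises the placebo side for those randomised to placebo first and the active side for those randomised to active first. These shifts offset if such users split evenly between sequences, but 10-20% of 30 is only 3 to 6 people, so an even split cannot be relied on. The section 9.b model has intervention and sequence terms but no period term.

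**Step 4: saturating response.** Mean effect = 0.5 × [(1 − p) + p·r]. Power is from the noncentral t with 29 degrees of freedom and noncentrality (mean effect) × √30.

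| Users p | Relative effect r | Mean effect | Noncentrality | Power |
|---|---|---|---|---|
| 0% | – | 0.500 | 2.74 | 75.4% |
| 10% | 0.5 | 0.475 | 2.60 | 71.0% |
| 20% | 0.5 | 0.450 | 2.46 | 66.4% |
| 10% | 0 | 0.450 | 2.46 | 66.4% |
| 20% | 0 | 0.400 | 2.19 | 56.3% |

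The plan's 80% is reached at an effect size of 0.53; at exactly 0.5 the exact figure is 75.4%, which is the baseline here. Adding the extra between-person variance, p(1 − p)[0.5(1 − r)]², changes the half-effect results only to 70.8% and 65.9%.

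**Step 5: total supplemental intake on active.** 6 + x = 6.3 to 8.0 g/d. It passes 7 g/d when x exceeds 1 g/d.

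**The case against.** The strongest reply is that the design protects itself. Each participant is their own control, so steady background use cancels. This stands. A reader might infer that the contrast is pulled toward zero whatever users do; Step 1 shows that it is not.

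A second reply concerns size. A reader might infer that 10-20% users reduce 30 completers to the equivalent of 30 × 0.9² = 24 or 30 × 0.8² = 19. That requires users to show no response at all, although they still receive the full 35 g/d fibre contrast, and the plan's synergy hypothesis gives no reason to expect none. At half effect the equivalents are 30 × 0.95² = 27 and 30 × 0.90² = 24.

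Third, continued own use might be read as defeating the washout. Section 4.c gives the washout the task of removing the previous period's intervention effect, and a return to a stable personal background achieves that.

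Fourth, section 5's description of the survey is abbreviated. It also omits antibiotics, alcohol, cannabis and relocation, all of which are criteria. The form itself and the consent pages are not available, so it cannot be said that participants are told nothing. This limits confidence, but the eligibility section should still carry the rule.

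Finally, the food frequency questionnaire and day-0 plasma values could reveal users. They could, but the plan states no action to take on the result.

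**Conclusion.** The gap in the written criteria is real: regular users of non-prescription EPA/DHA qualify, and the visible text does not govern their use during the trial. The consequence is conditional. There is no bias under steady use with an additive response, dilution if the response saturates, and a disturbed comparison if own use changes between periods or stops shortly before day 0. Under the assumed 10-20% users at half effect, power at effect size 0.5 falls from 75% to about 71-66%. The 56% figure is a worst case at 20% users with no response. Prevalence, own-product dose and degree of saturation are all assumptions.

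On total intake, a reader might infer that the plan permits an unsafe dose. The documents do not support that. Section 4.b reports 7 g/d as the top of the range studied, not as a limit, and says data are insufficient to set an upper intake. What can be said is that unrestricted own use on top of 6 g/d can exceed the cited range, and the passages need to be reconciled. No intake limit is proposed here.

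This is a worthwhile, inexpensive amendment and not a fatal flaw.

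**What to change.** - In Exclusion 2, extend the fish-oil entry to regular use of any EPA/DHA supplement, prescription or not. State a look-back before day 0 consistent with the 45-day clearance figure in section 4.c; without one, a volunteer who stops just before day 0 would still qualify. The existing threshold of more than once a week would continue to admit occasional users, so the sponsor should confirm that this is intended.
- Carry the same entry into the synopsis and add the item to the screening survey.
- Ask participants not to start such products from day 0 of period 1 to day 30 of period 2, including the washout, and confirm this with one question at study visits.
- Reconcile the 6 g/d study dose plus any own use with the range cited in section 4.b.

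The change should stay with n-3 products. Extending it to prebiotics or probiotics is tempting given Aim 2, but nothing examined here supports it or gives it a size.

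The cost is protocol wording, a survey item and a visit question. The downside is that a few volunteers become ineligible, which may slow recruitment slightly.
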